### Pilot trial data analysis

We will use Stata SE V.15 for Windows for all statistical analyses, and for data entry range checks for data values will be performed. We will report the recruitment of participants and the number of trial dropouts descriptively (frequencies and percentages). Further, we will report the means, SD and CI of the DDS and the other outcome measurements before and after the intervention period for both the intervention and control groups. As the study is a pilot and the sample size is small, we will not perform inferential statistics and analyse between-group calculations. The participants' PAID scores will be analysed descriptively (mean, SD), as well.

We will transcribe verbatim and analyse participants' and healthcare providers' experiences with the intervention by using thematic analysis. Thematic analysis is a flexible qualitative method without any specific theoretical foundation and consists of six steps: (1) transcribing, reading and rereading, (2) generating initial codes, (3) searching for themes, (4) reviewing themes, (5) defining and naming the themes, and (6) producing the report.

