### Planned data analysis for the evaluation study

To assess both short- and long-term effects of the intervention, we will collect one pre-intervention measure and two post-intervention (after 1 and 2 years) measures for both the intervention and control group. All analyses will be on an intention-to-treat basis, and we will compare intervention and control groups for each follow-up time using linear mixed effects models with DDS as the primary outcome measure. All models will define intervention, time and intervention-by-time interaction as fixed effects (all categorical), whereas a random intercept will be specified to account for correlated observations of the same individual (an exchangeable correlation structure assumed). To obtain  $p$  values or 95% CI for difference in DDS means between the comparison groups at different time points, we will perform a post-hoc test for pairwise comparison accounting for multiple testing. To test whether the predicted DDS means change differently over time, we will use the likelihood ratio test by comparing the log-likelihood between models with and without the intervention-by-time interaction. In linear mixed effects models, all available DDS measures for an individual will be used for estimation even though certain measures may be missing on follow-up for that individual. The model will produce unbiased estimates provided the data are missing at random. As this is a block-randomized trial, we will assume that the comparison groups are similar in all aspects except the treatment.

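### Does the descriptive-only pilot analysis leave the evaluation study without an effect estimate or variance figures that it needs?

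*SAP*

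**What the plan says.** Under the heading *Pilot trial data analysis*, the SAP states: "we will report the means, SD and CI of the DDS and the other outcome measurements before and after the intervention period", and this is "for both the intervention and control groups". Recruitment and dropout are to be given as counts and percentages, and interviews are analysed thematically. The SAP then rules out more: "we will not perform inferential statistics and analyse between-group calculations". It gives its reason: "As the study is a pilot and the sample size is small". No pilot sample size is stated.

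Under the heading *Planned data analysis for the evaluation study*, "we will collect one pre-intervention measure and two post-intervention (after 1 and 2 years) measures". Arms are compared at each follow-up time "using linear mixed effects models with DDS as the primary outcome measure". Arm, time and their interaction are categorical fixed effects, and a random intercept per person carries an exchangeable correlation. The interaction is tested by likelihood ratio. Neither section says that the pilot is to provide an effect estimate, an SD or a correlation for the evaluation study.

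**The concern.** Three things look wrong.

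- A confidence interval is an inferential statistic, so promising CIs and then excluding inferential statistics reads as a contradiction.
- The plan keeps intervals around four separate means and leaves out the interval for the contrast between arms. A reader may then set the before interval against the after interval within an arm. That ignores the pairing and mixes any effect of the intervention with time and regression to the mean.
- The evaluation study analyses repeated DDS scores, yet the pilot tables list neither the SD of within-person change nor the pre-post correlation. Recruitment and dropout percentages have no interval either.

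If the pilot were meant to supply these quantities, the evaluation study would be planned without a figure to which its sample size can be sensitive, and dropout from a small sample would look more certain than it is.

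**Working it through.** The SAP states no sample size, SD, effect size or correlation, so there is no figure of its own to reproduce. All values of the correlation ρ and of n below are assumed, with a marginal SD of 1 at each time.

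**1. Do the planned summaries give the paired variance?** SD of change = √(2(1−ρ)).

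| ρ | 0 | 0.3 | 0.5 | 0.7 | 0.9 |
|---|---|---|---|---|---|
| SD of change | 1.41 | 1.18 | 1.00 | 0.77 | 0.45 |

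They do not. The same two marginal SDs fit any of these values. This part of the concern is correct.

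**2. Does the evaluation model need that figure?** Not for its analysis. The model is fitted to the evaluation study's own DDS measurements, and its random-intercept and residual variances are estimated from them. Only sample-size planning could use a pilot value. The SAP does not give the pilot that task, and the basis for the sample size may lie in the protocol.

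**3. How would ρ enter the planned comparisons?**
- A sample size that scales with 1−ρ² would run from 0.84 (ρ = 0.4) to 0.36 (ρ = 0.8), a ratio of 0.84/0.36 = 2.3. That scaling belongs to a model with baseline as a covariate, and the planned model has none.
- With unconstrained arm-by-time means and complete data, the arm contrast at a follow-up time is the difference in follow-up means. Its variance is 2·SD²/n (n per arm), whatever ρ is.
- The interaction test does depend on ρ, through 1−ρ: 0.60 at ρ = 0.4 against 0.20 at ρ = 0.8, a ratio of 3.

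**4. How well would a small pilot fix ρ?** The Fisher interval is tanh(atanh(0.5) ± 1.96/√(N−3)), with N participants in total.
- N = 30: 0.17 to 0.73. On the 1−ρ scale this is 0.83 to 0.27, a ratio of 3.1.
- N = 60: 0.28 to 0.67. On the same scale this is 0.72 to 0.33, a ratio of 2.2.

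The pilot would therefore leave a range about as wide as the one it was meant to narrow, or only moderately narrower. The pilot section also does not say that its before-after interval matches the 1 and 2 years of the evaluation study, so the value might not carry over.

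**5. Is an effect estimate out of reach?** No. The follow-up difference and its CI follow from the two means, the two SDs and the arm sizes. The 95% half-width is t·√(2/n), in SD units.

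| n per arm | 10 | 15 | 20 | 30 |
|---|---|---|---|---|
| Half-width | 0.94 | 0.75 | 0.64 | 0.52 |

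Intervals this wide say little about the effect.

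**6. The before-versus-after reading.** Treating the two times as independent would overstate the SE of change by 1/√(1−ρ), which is 1.41 at ρ = 0.5 and 1.83 at ρ = 0.7. The plan makes no such comparison, so these ratios measure a possible misreading and not an error in a planned result.

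**7. Rates.** For an assumed 6 dropouts in 40 (15%), the exact 95% CI is 5.7% to 29.8%. That is wide, but anyone can compute it from the planned counts.

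**The case for a change.** The strongest case for a change accepts that a small pilot should not test efficacy. It argues that small numbers call for intervals in place of tests, and that they give no reason to print the less useful intervals and bar the more useful one. A difference rebuilt from published summaries is also unadjusted for baseline, and chance imbalance is likely in small arms. The interaction test is sensitive to ρ, so even an imprecise estimate, shown with its interval, has some value. The additions would cost a sentence and a few table columns.

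Part of this stands. The SD of change and the pre-post correlation are useful, cannot be recovered from the planned tables, and would be cheap to report. The word *inferential* is loosely used next to planned CIs.

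The rest does not make the plan wrong. The individual data will exist, so leaving a statistic out of a table does not lose it. A CI beside an arm mean shows precision, and the exclusion, which names between-group calculations in the same breath, most naturally means no hypothesis tests and no arm comparisons. A baseline-adjusted difference would have to be labelled as unfit for judging efficacy, so little is lost without it. It would also need more caution if the pilot is not randomised, since the SAP describes only the evaluation study as block-randomised.

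**Conclusion.** The concern does not call for a change. Followed as written, the pilot gives sound descriptive feasibility results, and no planned result is biased or miscalculated. Leaving out a between-arm estimate is a fair trade-off with a stated reason, and the illustrative half-widths of 0.52 to 0.94 SD agree with that reason. The missing SD of change and correlation are a reporting gap that an analyst can fill from data already held, as are intervals for the recruitment and dropout percentages. The clash between CIs and the exclusion of inferential statistics is a matter of wording.

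This rests on two points: the SAP assigns the pilot no role in supplying variances to the evaluation study, and all numerical illustrations use assumed sample sizes and correlations. If the protocol does base the evaluation study's sample size on the pilot, reporting the pre-post correlation would matter more. It could still be computed without altering the data collection or the evaluation model.

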### Planned data analysis for the evaluation study

To assess both short- and long-term effects of the intervention, we will collect one pre-intervention measure and two post-intervention (after 1 and 2 years) measures for both the intervention and control group. All analyses will be on an intention-to-treat basis, and we will compare intervention and control groups for each follow-up time using linear mixed effects models with DDS as the primary outcome measure. All models will define intervention, time and intervention-by-time interaction as fixed effects (all categorical), whereas a random intercept will be specified to account for correlated observations of the same individual (an exchangeable correlation structure assumed). To obtain  $p$  values or 95% CI for difference in DDS means between the comparison groups at different time points, we will perform a post-hoc test for pairwise comparison accounting for multiple testing. To test whether the predicted DDS means change differently over time, we will use the likelihood ratio test by comparing the log-likelihood between models with and without the intervention-by-time interaction. In linear mixed effects models, all available DDS measures for an individual will be used for estimation even though certain measures may be missing on follow-up for that individual. The model will produce unbiased estimates provided the data are missing at random. As this is a block-randomized trial, we will assume that the comparison groups are similar in all aspects except the treatment.

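### The planned DDS comparisons at years 1 and 2 make no use of baseline DDS; they are valid but less precise than the collected data allow

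*SAP*

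**What the plan says.** All of this stands in the SAP under the heading for the planned analysis of the evaluation study.

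- Measurements: "we will collect one pre-intervention measure and two post-intervention (after 1 and 2 years) measures for both the intervention and control group".
- Comparison: "we will compare intervention and control groups for each follow-up time using linear mixed effects models with DDS as the primary outcome measure". The results to be reported are p values or 95% intervals for the "difference in DDS means between the comparison groups at different time points", from post-hoc pairwise comparisons.
- Fixed effects: "All models will define intervention, time and intervention-by-time interaction as fixed effects (all categorical". No baseline DDS covariate is named, and the arms are not given a common mean at baseline.
- Covariance: "a random intercept will be specified to account for correlated observations of the same individual (an exchangeable correlation structure assumed".
- A separate test: "To test whether the predicted DDS means change differently over time, we will use the likelihood ratio test", which compares models with and without the interaction.
- Comparability of the arms: "As this is a block-randomized trial, we will assume that the comparison groups are similar in all aspects except the treatment".

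**The concern.** A model that holds the baseline value and a random intercept looks as if it adjusts for baseline. This one does not, as far as the reported contrasts go. Two arms at three times make six cells, and the fixed effects give six free means. One of the free quantities is a group difference at baseline, although randomisation makes that difference zero in expectation. Once it is free, the baseline data carry no information about the follow-up differences when data are complete.

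The difference at each follow-up is the effect the trial will report. Its interval will be wider than it need be. Seen conditionally, a chance baseline difference also carries over into the reported effect, in proportion to the within-person correlation. The likelihood ratio test treats baseline in another way, by subtracting it, so the two planned analyses could point in different directions after a chance imbalance.

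**Working it through.** **Inputs.** From the SAP: three measurement times, the fixed effects, the exchangeable structure and the reported contrast. The SAP gives no correlation, SD, sample size or power, so there is no figure of its own to reproduce. Assumed: correlation rho between any two DDS measures of one person, equal SD sigma at each time, and n per arm.

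**1. The planned contrast.** Generalised least squares for the six-mean model with complete data gives a variance of 2·sigma²/n for each follow-up difference, at every rho tried from 0.3 to 0.7. As a check, the planned model was fitted to simulated complete data (100 per arm, rho 0.6). It gave year-1 and year-2 differences of −0.00330 and −0.01887, equal to the raw mean differences.

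**2. The adjusted contrast.** With a common baseline mean, or with baseline as a covariate, the variance is 2·sigma²·(1 − rho²)/n. The variance ratio is 1 − rho² and the interval-width ratio is its square root. For power, a contrast with 80% power has an expected z of 1.96 + 0.84 = 2.80; after adjustment this becomes 2.80/√(1 − rho²).

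| rho | 1 − rho² | Interval narrower by | Power, from 80% |
|---|---|---|---|
| 0.3 | 0.91 | 5% | 0.836 |
| 0.5 | 0.75 | 13% | 0.899 |
| 0.6 | 0.64 | 20% | 0.938 |
| 0.7 | 0.51 | 29% | 0.975 |

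A null simulation of the year-1 comparison (20,000 runs, 60 per arm, rho 0.5) gave rejection rates of 4.9% unadjusted and 5.0% adjusted. The variances were 0.0334 and 0.0253, a ratio of 0.76 against 0.75 in theory.

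**3. With dropout.** Assume that 10% are lost by year 1 and 20% by year 2, completely at random. For rho 0.3, 0.5, 0.6 and 0.7, the ratios of adjusted to planned variance are:

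- year 1: 0.918, 0.769, 0.664, 0.536;
- year 2: 0.926, 0.787, 0.686, 0.561, which are cuts of 7%, 21%, 31% and 44%.

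**4. Given a chance imbalance.** Let the baseline difference be k standard errors and the true effect zero. The planned z statistic then has mean rho·k and variance 1 − rho². Rejection at the nominal 5% level is:

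| k | rho 0.3 | rho 0.7 |
|---|---|---|
| 0 | 4.0% | 0.6% |
| 1 | 5.0% | 3.9% |
| 1.96 | 7.9% | 20.5% |

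Averaged over randomisations it is 5.0%.

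**5. The interaction test.** This compares changes from baseline. With the same effect at both follow-ups, its noncentrality is proportional to 2/[3(1 − rho)]. That of a joint baseline-adjusted test is proportional to 2/[(1 − rho)(1 + 2·rho)]. The relative efficiency is (1 + 2·rho)/3, that is 0.533, 0.667, 0.733 and 0.800. It is below 1 for every rho below 1.

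**6. A trap in the remedy.** Suppose the correlations are 0.5 (baseline–year 1), 0.4 (baseline–year 2) and 0.7 (year 1–year 2). An exchangeable fit pools them to (0.5 + 0.4 + 0.7)/3 = 0.533. If the common baseline mean were added to that structure, the year-2 variance in units of 2·sigma²/n would be:

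- true: 1 + 0.533² − 2 × 0.533 × 0.4 = 0.858;
- as the model reports it: 1 − 0.533² = 0.716.

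The critical value is in effect 1.96 × √(0.716/0.858) = 1.79, and rejection is 7.3%. With baseline DDS as a covariate instead (20,000 runs, 100 per arm, same correlations), the year-2 variance ratio is 0.842 and rejection is 4.7%, the same as without adjustment.

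**The case against.** The strongest reply is that a free group-by-time mixed model is a recognised analysis of a randomised trial, and that preferring a more efficient valid estimator is an optimisation. It stands that this is no error of validity. It does not follow that the choice should be left: the baseline value is already collected, and the gain costs only wording.

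The size is wholly assumed. That also stands. At rho 0.2 the variance cut is only 1 − 0.96 = 4%. If correlation decays so that baseline and year 2 correlate at 0.4, the year-2 cut is about 16%, even where year 1 gains 25%.

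The fitted model also yields the interaction coefficients, which are differences in change from baseline and have variance factor 2(1 − rho). Against these, adjustment gains 20% at rho 0.6 (0.64/0.80) and 15% at rho 0.7 (0.51/0.60). But they are not the contrast the SAP says it will report, they are still less precise than the adjusted one, and below rho 0.5 they are less precise than the raw difference.

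The 5% error rate depends on equal SDs over time, because the model pools one variance. If the year-2 SD were 1.2 times the others, the pooled variance would be (1 + 1 + 1.44)/3 = 1.147 against a true 1.44, a ratio of 0.80, and rejection would be about 8%. This qualifies the concession made to the plan; it does not weaken the case for adjustment.

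Exposure to chance imbalance is the same loss seen conditionally, and should not be counted as a second defect. Finally, the sentence on block randomisation does not contradict the model and needs no rewording. It is, however, no reason to omit adjustment; it supports a common baseline mean.

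**Conclusion.** The concern holds. As specified, the follow-up differences in mean DDS take nothing from baseline DDS when data are complete, and with the dropout assumed above most of the gain from adjustment remains. The likelihood ratio test does not make up for this: it uses baseline inefficiently and gives no estimate or interval at each follow-up.

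The cost is precision: 9% to 49% of the variance for correlations from 0.3 to 0.7, less if the correlation is lower or decays by year 2. These figures rest on assumed correlations, equal SDs and, for the dropout case, loss completely at random. The plan should be changed, but its present contrast is not biased.

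**What to change.** Pre-specify the baseline-adjusted difference in mean DDS at years 1 and 2 as the primary estimate, in one of two ways.

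1. Keep baseline as an outcome and constrain the arms to a common baseline mean: categorical time, with intervention-by-time terms at years 1 and 2 only. Replace the present covariance line ("an exchangeable correlation structure assumed") with an unstructured within-person covariance. The common mean should not be combined with the exchangeable structure, for the reason in step 6 of the working.
2. Model years 1 and 2 only, with intervention, time, intervention-by-time, baseline DDS and baseline-by-time. State how a missing baseline DDS is handled; otherwise those participants drop out of the analysis, against the SAP's intention to use all available measures.

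The choice should be made before outcome data are seen, since adjustment adopted after an observed imbalance would be data-driven. The cost is the fixed-effects line, plus the covariance line for option 1 or a missing-baseline rule for option 2. No new data are needed.

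### The plan calls its estimates unbiased under missing at random alone, but with a fixed exchangeable covariance that claim, and the visit-specific intervals, also need the covariance to be right

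*SAP*

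**What the plan says.** The section *Planned data analysis for the evaluation study* sets out the model for the primary outcome, DDS.

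- **Visits:** "one pre-intervention measure and two post-intervention (after 1 and 2 years) measures for both the intervention and control group".
- **Mean model:** "All models will define intervention, time and intervention-by-time interaction as fixed effects (all categorical"). With two arms and three visits this leaves the six means unrestricted.
- **Covariance:** "a random intercept will be specified to account for correlated observations of the same individual (an exchangeable correlation structure assumed"). This means one variance and one correlation for all visits.
- **Missing data:** incomplete records are kept, "even though certain measures may be missing on follow-up for that individual", and "The model will produce unbiased estimates provided the data are missing at random".
- **Inference:** p values or a "95% CI for difference in DDS means between the comparison groups at different time points", adjusted for multiplicity, and a likelihood ratio test of the interaction.

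The section gives no alternative covariance, no robust standard error and no check of the structure. The software is named under *Pilot trial data analysis*: "We will use Stata SE V.15 for Windows for all statistical analyses".

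**The concern.** When a year-2 value is missing, maximum likelihood in effect predicts it from that person's earlier values, using the regression implied by the assumed covariance. Missing at random lets one ignore the dropout process, but it does not make that regression right. The mean model is saturated, so the covariance is the open condition. The plan labels it an assumption where it defines the model, but does not carry it into the unbiasedness claim.

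Two things are at stake, and they are separate:

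1. **Standard errors.** A random intercept imposes one common variance. If DDS spreads out or narrows over two years, the p value and interval at a given visit are miscalibrated, with or without missing data.
2. **Bias.** If the covariance is wrong and dropout depends on earlier DDS differently by arm, the prediction errors do not cancel in the group difference.

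A correct covariance is sufficient, not always necessary. There is no bias with complete data or with completely-at-random dropout.

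**Working it through.** The SAP gives no figure to reproduce on this point. The visits, mean model and covariance model are taken from the SAP. All variances, correlations and dropout rules below are assumptions.

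**Step 1. Standard error, complete data.** The exchangeable fit uses the average variance at every visit, so the ratio of true to model standard error at visit t is sqrt(var_t / mean variance). The true size of a nominal two-sided 5% test is 2Φ(−1.96/ratio).

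- Variances 0.8/1.0/1.2 (mean 1.0), year 2: ratio sqrt(1.2) = 1.095, size 2Φ(−1.789) = 7.4%, so the 95% CI covers 92.6%.
- Reverse order, year 2: ratio sqrt(0.8) = 0.894, size 2Φ(−2.191) = 2.8%, coverage 97.2%.
- Milder variances 0.9/1.0/1.1: 6.2%, and 3.9% reversed.
- At 2.5% per visit (critical value 2.241; Bonferroni over two follow-ups, if that were the unnamed method): 4.1% and 1.2% for 0.8/1.0/1.2 and its reverse.

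With equal variances the ratio is 1 whatever the correlations are.

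**Step 2. Bias, dropout at year 2 only.** Dropout is set by logit = −1 + slope × year-1 DDS, which gives 27–31% dropout. Baseline and year 1 are complete. For a fitted correlation ρ, the exchangeable model predicts year 2 with the same weight c = ρ/(1+ρ) on baseline and year 1. Let b21 and b01 be the true regression slopes of year 2 and of baseline on year 1. With no true effect, each arm's large-sample bias is

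[b21 − c(1 + b01)] × (mean year-1 DDS of those who stay).

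The bracket is zero if the covariance is truly exchangeable: with correlation 0.6, c = 0.375 and 0.6 − 0.375 × 1.6 = 0.

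Take slopes 0 and 1 in the two arms. Numerical integration gives year-1 means among stayers of 0 and −0.2554, for a year-1 SD of 1. The difference is the second arm minus the first.

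- AR correlation 0.7: fitted ρ 0.6416, c 0.3909; 0.7 − 0.3909 × 1.7 = 0.0355; × −0.2554 = −0.0091.
- Variances 0.8/1/1.2, correlation 0.6: c 0.3712; 0.6573 − 0.3712 × 1.5367 = 0.0869; × −0.2554 = −0.0222; divided by the year-2 SD of 1.095 = −0.0203.
- Correlations 0.4 (baseline with year 1), 0.75 (year 1 with year 2), 0.35 (baseline with year 2): c 0.3236; 0.75 − 0.3236 × 1.4 = 0.2970; × −0.2554 = −0.0758.

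Year-2 bias in year-2 SD units, no true effect, by dropout slopes in the two arms:

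| True covariance | 0.7 v 1 | 0.5 v 1 | 0 v 1 | −0.5 v 1 |
|---|---|---|---|---|
| AR 0.7 | −0.0025 | −0.0043 | −0.0091 | −0.0138 |
| AR 0.6 | −0.0031 | −0.0053 | −0.0112 | −0.0170 |
| Variances 0.8/1/1.2 | −0.0057 | −0.0097 | −0.0203 | −0.0309 |
| Variances 1.2/1/0.8 | +0.0067 | +0.0115 | +0.0240 | +0.0366 |
| SDs 1/1.15/1.3 | −0.0081 | −0.0141 | −0.0298 | −0.0457 |
| Correlations 0.4/0.75/0.35 | −0.0213 | −0.0364 | −0.0758 | −0.1158 |

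With the same slope in both arms the bias is 0. If there is a true effect of −0.3, it is 0.002–0.005 in absolute value, and 0.012 in the last pattern. Completely-at-random dropout gives 0, even at different rates by arm. An unstructured fit gives 0 throughout.

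**Step 3. Dropout possible at both follow-ups.** A simulation with 1,000,000 per arm let dropout depend on the last observed value, with 36–40% lost by year 2 and slopes of 0 v 1 or −1 v 1. True difference 0, bias in baseline SD:

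- AR 0.5–0.8: year 1 about −0.01 to −0.03, year 2 about +0.02 to +0.05.
- SDs 1/1.2/1.4: year 1 −0.03 to −0.10, year 2 −0.07 to −0.19.
- Unstructured fit: at most about 0.003, which is simulation noise.

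The sign for AR differs from step 2, so neither the direction nor a ceiling can be predicted without knowing the dropout pattern.

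**The case against.** **The assumption is disclosed and conventional.** The unbiasedness sentence refers to the model just defined, and a random intercept for three visits is common. True, but a reader is told that only the missingness assumption matters, and nothing guards against the other one failing.

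**The bias needs two conditions at once.** The covariance must be wrong and dropout must depend on DDS differently by arm. Nothing in the SAP suggests the latter. This stands. At 100 per arm the practical effect can be slight: rejection was 5.9% for AR 0.7 with slopes −0.5 v 1, and 4.6% for correlations 0.4/0.75/0.35 with slopes 0.7 v 1.

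**The 7.4% is a single unadjusted test, while the plan adjusts for multiplicity.** This also stands in part. With complete data, correlation 0.6 and Bonferroni over two follow-ups, the chance of any false positive is 5.9% for variances 0.8/1.0/1.2. It is 4.5% with equal variances and 3.4% in the reverse order. Over three time points it is at most 4.6%. Family-wise error is therefore disturbed less than the single test, but the year-2 interval is still wrong.

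**The remedy has an assumption of its own.** A common unstructured covariance is biased if the arms' covariances differ. With correlations of 0.6 v 0.5, 0.6 v 0.4 or 0.7 v 0.4 and the same dropout rule in both arms, the bias is about 0.015, 0.03 and 0.05 SD. The exchangeable model has the same bias there, so this is no reason to keep it.

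**Conclusion.** The concern holds. Missing at random does not by itself give unbiased group differences under the covariance the plan fixes, and the visit-specific intervals also depend on equal variances over time.

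The size in this trial cannot be stated, because the SAP gives no SD, correlation, dropout rate or sample size. Under the assumed patterns:

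- The year-2 test at nominal 5% ranges from 2.8% to 7.4% with complete data. This needs only a variance that changes over time.
- The bias is usually a few hundredths of an SD or less. It reaches about 0.12 SD with year-2 dropout only, and about 0.19 baseline SD with rising variance and opposite dropout rules in the two arms.

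This is not evidence that the result will be biased. It is an avoidable restriction on the primary analysis, supported by an incomplete statement, and it should be changed.

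**What to change.** 1. Replace the random intercept by an unstructured residual covariance over the three visits. In the named software: `mixed ... || id:, noconstant residuals(unstructured, t(time))`.
2. Reword the missing-data sentence to say that estimates are unbiased if data are missing at random and the mean and covariance models are correctly specified.
3. Name the exchangeable model with robust standard errors only as a fallback for non-convergence. Robust standard errors repair the intervals, not the bias.
4. Optionally, use REML with small-sample degrees of freedom for the visit-specific differences. The likelihood ratio test of the interaction must stay on maximum likelihood.

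**Cost.** The change is one model option and one sentence. It estimates six covariance parameters instead of two. If exchangeability is in fact true, the SD of the year-2 difference rises by about 0.1–0.4% at 50–200 per arm (assumed sizes). The maximum likelihood Wald test is slightly liberal in small samples: 5.6–6.4% at 50 per arm and 5.3–5.7% at 100 per arm. That is the only reason for step 4.

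### Does the planned mixed model, which relies on missing at random, contradict the intention-to-treat claim and overstate the year-1 and year-2 effects?

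*SAP*

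**What the plan says.** Everything at issue is in the SAP section 'Planned data analysis for the evaluation study'. It sets the principle: "All analyses will be on an intention-to-treat basis". It sets the schedule: "one pre-intervention measure and two post-intervention (after 1 and 2 years) measures for both the intervention and control group". The analysis uses "linear mixed effects models with DDS as the primary outcome measure", with arm, visit and their interaction as categorical fixed effects, and "a random intercept will be specified to account for correlated observations of the same individual".

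On missing DDS, the section says that "all available DDS measures for an individual will be used for estimation even though certain measures may be missing on follow-up for that individual", and then gives the condition: "The model will produce unbiased estimates provided the data are missing at random". It says nothing more about missing DDS. It gives no expected dropout rate, effect size, SD, within-person correlation or sample size. It does not say whether people who stop the intervention continue to be measured.

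**The concern.** Intention-to-treat suggests the effect in everyone randomised, including those who leave. A mixed model with a separate mean for each arm and visit does not observe those who are missing. It treats a person missing from the intervention arm as following that arm's observed course, adjusted for the person's own earlier scores. If people who leave the intervention lose its benefit, the model describes something closer to the effect had everyone stayed. The estimate would then be too large as an effect in all randomised participants, and its confidence interval would cover that effect too rarely. A better covariance structure would not help, because the trouble lies in the means. If one arm lost more people than the other because their distress was worsening, a difference could even appear where there is none. The plan names one assumption, relies on it at both follow-ups, and includes no analysis in which it fails.

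**Working it through.** The SAP gives no figure to reproduce, so the check has two parts: what the arithmetic shows under assumed values, and whether the text supports those assumptions.

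**Arithmetic.** Let D be the arm difference that the model targets (negative means benefit). Let d_I and d_C be the dropout shares in the intervention and control arms. Let δ_I and δ_C be the amounts by which leavers' true DDS exceeds what the model predicts for them. Then

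- effect in all randomised = D + d_I·δ_I − d_C·δ_C.

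The inputs below are all assumed, in SD units:

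| Case | Inputs | Effect in all randomised | Model reports |
|---|---|---|---|
| Intervention leavers lose all benefit, control leavers as predicted | D = −0.40, d = 0.20 in both arms, δ_I = 0.40, δ_C = 0 | −0.40 + 0.08 = −0.32 | −0.40 (ratio 1.25) |
| Leavers in both arms worsen equally | as above, δ_I = δ_C = 0.30 | −0.40 + 0.06 − 0.06 = −0.40 | −0.40 (no bias) |
| Only control leavers worsen | as above, δ_I = 0, δ_C = 0.30 | −0.40 − 0.06 = −0.46 | −0.40 (understated) |
| Leavers as predicted (missing at random) | δ_I = δ_C = 0 | −0.40 | −0.40 (no bias) |

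In the first case the ratio is 1/(1−d): 1.11 at 10%, 1.25 at 20% and 1.43 at 30%. A simulation of the planned random-intercept model (40,000 people, assumed intraclass correlation 0.6, assumed effect −0.30 SD) gave year-2 ratios of 1.13, 1.26 and 1.48, in line with the formula apart from simulation noise. When year-2 leavers had already lost the benefit at an observed year-1 visit, the ratios fell to 1.11, 1.21 and 1.38, because the model uses the earlier score. When missing at random held, they lay between 0.99 and 1.02.

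**Coverage and test size.** In the first case at 20% loss, the bias is 0.40 × 0.20 = 0.08 and the SE is √(2/(0.8n)). Coverage of a 95% interval is 92.0%, 89.0% and 85.8% for an assumed n of 100, 200 and 300 per arm. For no true effect, 20% against 10% loss, and leavers 0.5 SD worse than predicted, the bias is (0.20 − 0.10) × 0.5 = 0.05 and the SE is √(1/(0.8n) + 1/(0.9n)). Test size is 6.2%, 7.5% and 8.7%. These figures use the unadjusted critical value 1.96, whereas the SAP adjusts its pairwise comparisons for multiplicity by a method it does not name. With Bonferroni over two follow-ups (an assumption; critical value 2.241), coverage is 95.6%, 93.5% and 91.3% against a nominal 97.5%. Size per comparison is 3.3%, 4.1% and 4.9% against a nominal 2.5%. Distortion remains under the assumed scenario, but the unadjusted percentages do not describe the planned intervals.

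**Text.** Three readings decide the point.

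1. *Is a sentence false?* No. Unbiasedness is claimed only under missing at random, and every biased case above breaks that condition.
2. *Does the model contradict intention-to-treat?* No. Someone who stops the intervention but still completes the DDS contributes those scores to the randomised arm, because all available measures enter. The gap opens only if stopping the intervention and missing a measurement are the same event. The SAP does not say that they are, and follow-up after stopping is commonly a protocol matter.
3. *Does the scenario fit the design?* Not clearly. Both follow-ups are described as post-intervention. Read literally, a person missing at year 1 or year 2 may have completed the intervention and only missed an assessment, so an effect that holds while engaged and vanishes on leaving has no evident basis in the text.

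**The case for a change.** The strongest opposing case is that handling missing primary-outcome data belongs in a SAP, and this one settles it with a single assumption that the data cannot verify. The assumption bears most on the two-year comparison, where losses are likely to be greatest. A supporting analysis would need no new data, and choosing it in advance avoids selecting it after dropout by arm has been seen. All of that is fair, and it stands as advice: the plan examines no departure from missing at random, so its result alone would not show whether the conclusion depends on that assumption.

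It does not make the plan wrong. The primary estimate would be unchanged. The usual remedy, imputing intervention-arm leavers from the control-arm profile, is one choice among several. Making a claim of robust benefit depend on it is a rule on which reasonable statisticians differ. It would also do little about the no-effect case above. If the full-arm means are equal, those who stay differ by −0.05, and the control-based estimate is 0.8 × (−0.05) = −0.04, which removes a fifth of the bias. If the means of those who stay are equal, it removes none.

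**Conclusion.** The concern does not hold. The overstatement factor 1/(1−d) is correct where intervention-arm leavers lose all benefit, control-arm leavers follow prediction, and leavers are no longer measured. The SAP supports none of these conditions, and it gives no dropout rate or effect from which a size could be derived. Under other equally possible conditions the bias is zero or runs the other way. The plan states the assumption it relies on, and its use of all available measurements by randomised arm is compatible with intention-to-treat. What remains is a preference for an added sensitivity analysis. This conclusion rests on the SAP alone; if the protocol ends DDS measurement when someone stops the intervention, the case for that analysis becomes stronger, but no statement in the SAP becomes false.
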